8.1.3.2 Baseline Functional and Behavioral Assessments

Participants will receive a unique URL link by e-mail to complete the following functional and behavioral assessments electronically through the LORIS survey tool. Site study staff may also be available by phone/video-call to assist participants in completion of these questionnaires if preferred. Paper versions of the questionnaires may also be sent to participants by mail to complete at home and return to the site if preferred or requested by the participant. (Total estimated time: 30 minutes):

- Geriatric Depression Scale (GDS)
- Generalized Anxiety Disorder 7-Item Scale (GAD-7)
- Sleep Disorders Questionnaire
- COVID-19 Impact Survey
- Research Satisfaction Survey

The following questionnaire will be completed by study partner (if available).

- Mild Behavioral Impairment Checklist (MBI-C) (estimated time: 10-15 minutes)

8.1.4 ***Additional Remote Baseline Testing***

Following completion of the baseline procedures above, participants will also complete the following assessments remotely within approximately 2 weeks:

- BHPro registration and completion of lifestyle risk questionnaires and goal setting (estimated time to complete is 1.0 hour; see section [8.3](#))
- Weekly participation in BHPro (approximately 40 minutes/week)
- “Burst” Cognitive Testing (5-10 minutes/day for 6 consecutive days following initial testing at Baseline Visit)
- Cogniciti Brain Health Assessment (estimated time to complete is 20 minutes)
- Actigraphy recording (continuous recording for 14 consecutive days)
- EEG recording (nightly recordings for 3 consecutive nights)

8.1.5 ***Month 3 Remote Follow-Up and Testing***

Participants will receive a follow-up phone call from a site study team member at approximately month 3 following baseline to assess continued interest in BHPro participation and satisfaction with BHPro.

Participants will also receive notifications to complete the following activities remotely at month 3:

- Notification via the MyCogHealth app will be sent to participant to complete “Burst” Cognitive Testing (estimated time: 5-10 minutes/day for 7 consecutive days)
- Lifestyle risk questionnaires and goal setting within BHPro (estimated time: 20-30 minutes; see section [8.3](#))

8.1.6 **Month 6 Remote Follow-Up and Testing**

Participants will receive a follow-up phone call from a site study team member at approximately month 6 following baseline to assess continued interest in BHPro participation, and review any medical, lifestyle and diagnostic changes that have occurred since the baseline visit. The phone call will take an estimated 0.5-1.0 hours to complete.

Participants will also complete the following cognitive assessments remotely:

- Notification via the MyCogHealth app will be sent to participant to complete “Burst” Cognitive Testing (estimated time: 5-10 minutes/day for 7 consecutive days)
- Study coordinator will send participant an email that contains a personalized link to complete the Cogniciti Brain Health Assessment (estimated time: 20 minutes)
- BHPro outcome assessments (program usability and acceptability, dementia literacy, self-efficacy, attitudes toward dementia; see section [8.3](#)). These will be completed online within BHPro (estimated time: 30-45 minutes)
- Lifestyle risk questionnaires and goal setting within BHPro (estimated time: 20-30 minutes)

8.1.7 **Month 9 Remote Follow-Up and Testing**

Participants will receive a follow-up phone call from a site study team member at approximately month 9 following baseline to assess continued interest in participation and satisfaction with BHPro.

Participants will also receive notifications to complete the following activities remotely at month 9:

- Notification via the MyCogHealth app will be sent to participant to complete “Burst” Cognitive Testing (estimated time: 5-10 minutes/day for 7 consecutive days)
- Lifestyle risk questionnaires and goal setting within BHPro (estimated time: 20-30 minutes)

8.1.8 **Month 12 Remote Visit**

Participants will complete the following procedures remotely via video-conference with a member of the study team at approximately Month 12 for a remote re-assessment.

Study participants will undergo the following procedures (Estimated Time to Complete: 4.0-5.0 hours):

- Documentation of changes to medical history (including medication changes and any medical procedures) that have occurred since the time of the last assessment
- Self-report weight
- Body Mass Index (BMI) calculation (based on self-report current height and weight)
- Brief Remote Neurological Exam (completed by Site Principal Investigator or qualified medical professional)
- Lawton Brody IADL
- MoCA
- CDR (if a study partner is not available, the CDR score will be decided by site-level research team consensus based on all other available information and utilizing best clinical judgement.)
- Neuropsychological Test Battery (see section [10.1.4](#))
- Instructions and application of wearables for actigraphy and EEG recordings (see section [9.3](#))

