8.1.8.2 Month 12 Remote Testing

Participants will also complete the following assessments remotely within approximately 2 weeks:

- “Burst” Cognitive Testing (estimated time: 5-10 minutes/day for 7 consecutive days)
- Cogniciti Brain Health Assessment (estimated time: 20 minutes)
- Actigraphy recording (continuous recording for 14 consecutive days)
- EEG recording (nightly recordings for 3 consecutive nights)
- BHPro outcome assessments (program usability and acceptability, dementia literacy, self-efficacy, attitudes toward dementia). These will be completed online within BHPro (estimated time: 30-45 minutes)
- Lifestyle risk questionnaires and goal setting within BHPro (estimated time: 20-30 minutes)

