12.0 ADVERSE EVENTS

An adverse event (AE) is any untoward medical occurrence in a participant that occurs from the time of the baseline visit and up to 30 days after study participation has ended. For the purposes of reporting on the CTU study, an AE is defined as any unfavourable or unintended sign (e.g., including an abnormal laboratory finding), symptom, or disease associated with study procedures that are both **non-serious and either temporally or causally related to study procedures**. Pre-existing conditions, which increase in frequency or severity or worsen in nature during, or as a consequence of, a study procedure, may also be considered an AE if it meets the definition of being both non-serious and related to a study procedure.

An AE **does not** include:

- Medical or surgical procedures (e.g., surgery, endoscopy, tooth extraction, transfusion). The condition that leads to the procedure is the AE.
- Situations where an untoward medical occurrence has not occurred (e.g., hospitalization for elective surgery, social and/or convenience admissions).
- Worsening of symptoms associated with expected decline in memory or an associated co-morbid condition and not related to a study procedure.
- Those medical or surgical adverse events that are not related to the study procedures

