12.1 Evaluation and Reporting of Adverse Events

All AEs both non-serious and either temporally or causally related to study procedures (i.e., a new event or an exacerbation of a pre-existing condition) that occur from the baseline visit and up to 30 days after study participation has ended will be recorded as an AE in LORIS. Adverse events that occur prior to the baseline visit will be documented as medical history. The Investigator must follow all AEs until the AE resolves, or until the Investigator determines the event is chronic or clinically stable. If an AE remains unresolved at the conclusion of participation in the BHSP, the Investigator will make a clinical assessment to determine whether continued follow-up of the AE is warranted.

The Investigator should attempt to establish a diagnosis of the event based on signs, symptoms and/or other clinical information. In such cases, the diagnosis should be documented as the AE and not the individual signs/symptoms.

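### The scheduled contacts do not cover the adverse-event window: the Month 3 and Month 9 calls omit medical changes, and nothing is asked after the Month 12 home procedures

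*Protocol*

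**What the plan says.** **Window.** Section 12.0 defines an AE as an untoward occurrence that "occurs from the time of the baseline visit and up to 30 days after study participation has ended". Section 12.1 says that qualifying events "that occur from the baseline visit and up to 30 days after study participation has ended will be recorded as an AE in LORIS". To be reportable, a non-serious event must be linked to study procedures in time or by cause. Section 12.3 uses the same window for serious events.

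**Contacts after baseline.**
- Month 3 call (Section 8.1.5): made "at approximately month 3 following baseline to assess continued interest in BHPro participation and satisfaction with BHPro".
- Month 6 call (Section 8.1.6): also to "review any medical, lifestyle and diagnostic changes that have occurred since the baseline visit".
- Month 9 call (Section 8.1.7): made "at approximately month 9 following baseline to assess continued interest in participation and satisfaction with BHPro".
- Month 12 visit (Section 8.1.8): "Documentation of changes to medical history (including medication changes and any medical procedures) that have occurred since the time of the last assessment".
- End of Study visit for early leavers (Section 8.1.9): ideally everything done at Month 12. If the participant will not do it all, the BHPro outcome assessments and then the lifestyle questionnaires take priority.

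Appendix 2 agrees. After screening, medical history is marked only at Months 6 and 12, footnote 5 confines the medical part of the calls to Month 6, and there is no AE row.

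**Home procedures.** Section 8.1.4 places 14 days of actigraphy, 3 EEG nights and the remaining burst sessions in roughly the two weeks after the baseline visit. Section 8.1.8.2 repeats them after the Month 12 visit: "Participants will also complete the following assessments remotely within approximately 2 weeks". No contact is listed after that.

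**The concern.** Reportable AEs must be tied to study procedures, and the wearables are used only in two short blocks, just after baseline and just after the Month 12 visit. The medical reviews fall well after the first block and before the second.

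The harms foreseen in Section 5.5.1 are mild and short-lived: fatigue or frustration with testing, low mood after questionnaires, and discomfort or disturbed sleep from the devices. Such events are easily forgotten, yet Section 12.2 asks for onset and resolution dates, severity and relatedness. The cohort may include people with MCI, for whom low delayed story recall is among the criteria (Appendix 1C), and a study partner is optional (Section 8.1.2.1).

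What is at stake is how a low AE count can be read. If few events are recorded, the reader cannot tell whether few occurred or few were asked about. That matters somewhat for a programme that the protocol hopes to offer to the public.

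**Working it through.** The plan gives no figure for this point, so there is none to reproduce. The check is calendar arithmetic on the schedule.

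**Inputs**
- One month = 365.25 / 12 = 30.44 days, so Month 6 is day 182.6 and Month 3 is day 91.3.
- Visit window at Months 3, 6 and 12: plus or minus 14 days (Appendix 2).
- End of the baseline home block, *s*: day 14 if 14 days of actigraphy start at once, or day 28 if baseline procedures use their full 14 days (Section 8.1.3.1) and the home block follows over about two weeks (Section 8.1.4).

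**Lag from the end of the baseline home block to the first medical review**

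Lag = (182.6 + *w* − *s*) / 30.44, with *w* = −14, 0 or +14 days.
- *s* = 28: 140.6 / 30.44 = 4.6; 154.6 / 30.44 = 5.1; 168.6 / 30.44 = 5.5 months.
- *s* = 14: 154.6 / 30.44 = 5.1; 168.6 / 30.44 = 5.5; 182.6 / 30.44 = 6.0 months.

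The range is 4.6 to 6.0 months. Events early in the block, such as those on the EEG nights, wait a little longer.

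**Lag if the Month 3 call asked (nominal dates)**
- *s* = 28: (91.3 − 28) / 30.44 = 2.1 months.
- *s* = 14: (91.3 − 14) / 30.44 = 2.5 months.

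**What a Month 9 question would add.** If the 7-day Month 6 burst starts at the Month 6 call, its end precedes the Month 12 review by (182.6 − 7) / 30.44 = 5.8 months. A Month 9 question cuts this to (91.3 − 7) / 30.44 = 2.8 months.

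**After the Month 12 visit.** Home procedures run for about 14 days. If participation ends with the last of them, the window stays open for 30 more: 14 + 30 = 44 days with no scheduled question.

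**Early leavers.** The full End of Study visit carries the Month 12 medical-history review. The reduced set in Section 8.1.9 does not.

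**The case against.** The strongest case on the other side is that the text, Appendix 2 and footnote 5 agree, so this is a deliberate choice in a study whose risks are called minimal. AEs are not an outcome, and the SAP plans no AE analysis. Section 12 requires every qualifying event to be recorded, however it comes to light, and operational detail is left to a manual that is not among the documents. All of this stands, and it keeps the point minor. It does not supply a scheduled question inside the stated window.

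Some stronger readings are tempting but unsupported:
- A reader might infer that events from all baseline and Month 12 procedures go unasked. The neuropsychological battery is given live by video, so staff can see fatigue or frustration at the time. Only the home procedures fit.
- A reader might infer that events after Month 12 cannot be captured. Participants can report on their own initiative, and the device card gives staff contact details (Sections 9.3.1 and 9.3.2), though it is offered for questions.
- A reader might count everyone who drops out before Month 6 as never asked. Section 8.1.9 encourages continued visits and otherwise offers an End of Study visit, so such a count would be a ceiling.
- A reader might want to state what share of events is forgotten. No document gives a recall rate, so any percentage would only restate an assumption.

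In the other direction, the Month 6 and Month 12 items concern medical changes and are not described as AE queries. Solicited AE capture may therefore be weaker than two reviews suggest.

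**Conclusion.** The point holds as a minor mismatch between the AE window in Section 12 and the contact schedule in Section 8.1 and Appendix 2. Events from the baseline home procedures are first asked about 4.6 to 6 months after those procedures end. Events from the same procedures after the Month 12 visit are not asked about at any scheduled contact, over about 44 days.

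This rests on three assumptions: the baseline home block ends between day 14 and day 28, participation ends with the last Month 12 procedure, and the Study Procedures Manual contains no AE prompt. If it does contain one, a cross-reference in Section 12 and Appendix 2 is enough. The documents do not show how many events would be missed, and no such number is claimed.

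**What to change.** 1. In Sections 8.1.5 and 8.1.7, add one standard question on study-procedure-related AEs to the existing Month 3 and Month 9 calls. Show it in a new AE row in Appendix 2 and amend footnote 5 to match.
2. Send one AE item through the existing LORIS survey link (Section 10.2) at the end of the 30 days that follow the Month 12 procedures.
3. Include the AE question in the reduced End of Study set in Section 8.1.9.
4. If follow-up is already complete, any AE report should state that medical changes were reviewed only at Months 6 and 12 (or End of Study), and that nothing was solicited after the Month 12 home procedures.

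The full Month 6 medical review should not be copied to the other calls. Section 8.1.6 puts the call that contains it at 0.5 to 1.0 hours. If both other calls took that long for 350 participants, the ceiling would be 350 × 2 × 0.5 = 350 to 350 × 2 × 1.0 = 700 call-hours. The review would also gather many events that Section 12.0 excludes as unrelated to study procedures.

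The cost is a short question on two calls that already take place, one survey item, some protocol wording, and somewhat more minor AEs to enter.

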8.1.8.1 Month 12 Functional and Behavioral Assessments

Participants will receive a unique URL link by e-mail to complete the following functional and behavioral assessments electronically through the LORIS survey tool. Site study staff may also be available by phone/video-call to assist participants in completion of these questionnaires if preferred. Paper versions of the questionnaires may also be sent to participants by mail to complete at home and return to the site if preferred or requested by the participant. (Total estimated time: 30 minutes):

- Geriatric Depression Scale (GDS)
- Generalized Anxiety Disorder 7-Item Scale (GAD-7)
- Sleep Disorders Questionnaire
- COVID-19 Impact Survey
- Research Satisfaction Survey

The following questionnaire will be completed by study partner (if available).

- Mild Behavioral Impairment Checklist (MBI-C) (estimated time: 10-15 minutes)

8.1.8.2 Month 12 Remote Testing

Participants will also complete the following assessments remotely within approximately 2 weeks:

- “Burst” Cognitive Testing (estimated time: 5-10 minutes/day for 7 consecutive days)
- Cogniciti Brain Health Assessment (estimated time: 20 minutes)
- Actigraphy recording (continuous recording for 14 consecutive days)
- EEG recording (nightly recordings for 3 consecutive nights)
- BHPro outcome assessments (program usability and acceptability, dementia literacy, self-efficacy, attitudes toward dementia). These will be completed online within BHPro (estimated time: 30-45 minutes)
- Lifestyle risk questionnaires and goal setting within BHPro (estimated time: 20-30 minutes)

8.1.9 End of Study Remote Visit (Early Discontinuation)

Participants who have logged in and completed the registration process for BHPro but choose to withdraw and/or discontinue participation (see also: section [11.0](#) Early Discontinuation Procedures) in the BHPro Intervention for any reason will have the opportunity to complete further study visits per protocol up to the end of the study with their ongoing consent. Their continued participation should be encouraged to address the impact of early discontinuation compared to completion of the BHPro Intervention. If a participant declines to complete further study visits per protocol, an End of Study Remote Visit will be completed as close as possible to the time of study discontinuation. Ideally, the End of Study Remote visit will include all of the procedures and assessments described in the Month 12 Remote Visit (section [8.1.8](#)). If the participant is not willing to complete all of the procedures and assessments, the BHPro outcome assessments (program usability and acceptability, dementia literacy, self-efficacy, attitudes toward dementia) should be prioritized. These will be completed online within BHPro (estimated time: 30-45 minutes). An additional priority is completion of the Lifestyle risk questionnaires and goal setting within BHPro (estimated time: 20-30 minutes). For further detail please refer to the Study Procedures Manual.

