Information is organized as chapters within the modules, which contain scientific evidence, explanation of principles and mechanisms that underlie positive effects, specific recommendations (e.g., type and dose of prescribed physical exercises), suggestions to improve behavior in everyday life and typical barriers and tips to circumvent them. Content format will include visual and auditory text, pictures, animations, quizzes, questionnaires and interactive exercises.

8.3.2 **Personalized Profiles on Modifiable Lifestyle Risk Factors**

Participants will be asked to complete brief online lifestyle risk questionnaires approximately every 3 months (see [Appendix 3](#) for descriptions of the BHPro Lifestyle Risk Questionnaires). Questions will be related to the content in the program modules (e.g. sleep, diet, physical activity, cognitive engagement, social and psychological health, sensory). A personalized profile will be developed for each participant based on their responses to the lifestyle questionnaires. Participants will also be asked to set goals based on their risk profile and to re-visit and update their goals every three months. Participants will be encouraged to focus on the content modules that are related to their risk profile. Although participants will have access to all content modules within the program, modules that are suggested to the participant based on their risk profile will be highlighted.

8.3.3 **BHPro Outcome Variables and Data Collection**

The following data and assessments will be collected directly through BHPro. For more detailed information on the specific instruments see section [10.0](#). (Study Specific Instruments):

Outcome	Measure/Data Collected	Frequency
Engagement using BHPro	Direct monitoring of several parameters that could include: - Dates and time of program use - % completion of chapters at regular intervals - % completion of questionnaires - Other parameters may be added to this list as the studies goes on	Weekly/monthly
Acceptability (usefulness and ease of use) of BHPro	Adapted version of the Technology Acceptance Model questionnaire	Every 6 months
Usability of the BHPro	Adapted web-based version of the System Usability Scale (SUS)	Every 6 months
Dementia Literacy	Alzheimer Disease Knowledge Scale (ADKS)	Every 6 months
Participant Self-Efficacy	General Self-Efficacy Scale (GSE)	Every 6 months

Outcome	Measure/Data Collected	Frequency

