10.3 BHPRO Outcome Measures

The following assessments will be completed online directly through BHPRO. Participants will receive an e-mail notification to login into BHPRO to complete the following assessments.

10.3.1 *Alzheimer’s Disease Knowledge Scale (ADKS)*

The Alzheimer’s Disease Knowledge Scale is a 30-item, true/false scale that was designed to assess knowledge about Alzheimer’s disease among laypeople, patients, caregivers, and professionals. It covers risk factors, assessment and diagnosis, symptoms, course, life impact, caregiving, and treatment and management [41]. This scale will be completed online within BHPRO to measure changes in dementia literacy.

10.3.2 *The General Self-Efficacy Scale (GSE)*

Self-Efficacy is a concept that refers to one's global confidence in their ability to cope with demanding or novel situations. The General Self-Efficacy scale is a 10-item, 4-point scale which measures one's perceived competence in dealing with a range of stressful or challenging situations [42]. The scale will be completed online within BHPro.

10.3.3 ***Perceptions Regarding Investigational Screening for Memory in Primary Care (PRISM-PC)***

Sections B and D of the PRISM-PC questionnaire will be used to assess attitudes toward dementia and dementia screening and will be completed online within BHPro. The PRISM-PC questionnaire captures participants' acceptance, perceived harms, and perceived benefits of dementia screening [43].

10.3.4 ***System Usability Scale (SUS)***

The SUS [44] is a simple scale giving a global view of subjective assessments of usability. An adapted 11-item version of the SUS will be used to measure usability of BHPro.

10.3.5 ***Technology Acceptance Model Questionnaire***

A web-based adapted version of the Technology Acceptance Model Questionnaire [45] will be used to evaluate user acceptance of BHPro. Questions include attitude, perceived usefulness and perceived ease of use of the technology.

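### Participants who stop BHPro have one written route for giving the primary outcome, which is to log back into BHPro; a fallback route already exists for less central questionnaires

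*Protocol*

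**What the plan says.** Protocol 8.1.9 applies to "Participants who have logged in and completed the registration process for BHPro but choose to withdraw and/or discontinue participation" in the intervention. They are encouraged to continue all visits, so that early discontinuation can be compared with completion. Those who decline are to have an exit visit modelled on Month 12. If they will not do all of it, "the BHPro outcome assessments (program usability and acceptability, dementia literacy, self-efficacy, attitudes toward dementia) should be prioritized", and these are done online within BHPro. The section then goes on: "An additional priority is completion of the Lifestyle risk questionnaires and goal setting within BHPro".

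Section 10.3 gives the general route for the BHPro outcome measures: "Participants will receive an e-mail notification to login into BHPRO to complete the following assessments". For the ADKS it adds: "This scale will be completed online within BHPRO to measure changes in dementia literacy". Sections 8.1.6 and 8.1.8.2 say the same for Months 6 and 12, and section 8.3.1 requires an e-mail address and password to log in.

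The GDS, GAD-7, sleep, COVID-19 and research satisfaction questionnaires are handled differently. Section 8.1.8.1 offers a LORIS link, help by phone or video call, and a third option: "Paper versions of the questionnaires may also be sent to participants by mail to complete at home".

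Goal setting is described in section 8.3.2, under the BHPro intervention: "Participants will also be asked to set goals based on their risk profile". The same section has participants revisit their goals every three months and highlights suggested modules according to the risk profile.

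SAP 8.1 assumes data are missing at random and multiply imputes the ITT sample. Its sensitivity analyses fit the model to observed data in the mITT and Completers samples.

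**The concern.** Stopping the programme and failing to provide an ADKS score can share one cause: unwillingness to open BHPro. A stopper who would answer a short e-mailed or paper form but will not log in can still supply a GDS, a GAD-7 and the neuropsychological battery, yet no ADKS, GSE, PRISM-PC or lifestyle score. If such people gained less knowledge than those who stayed, the observed change is too favourable. In a single-group study there is no control arm in which a similar loss could offset it. It also works against the protocol's own reason for following stoppers.

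A second, smaller matter is that stoppers are asked to do goal setting at their assessment. That offers them again a component of the intervention they left. It bears mainly on the lifestyle outcomes of stoppers who remain in follow-up.

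**Working it through.** **1. The plan's own figures.** Protocol 13.1 starts from 350 participants with 20–30% dropout: 350 × 0.80 = 280 and 350 × 0.70 = 245 completers, so 70 to 105 people are lost. Appendix 4 gives n = (1.96 + 0.84)² × 2(1 − r)/ES² + 2. For ES = 0.2:
- r = 0.3: 7.84 × 1.4/0.04 + 2 = 276.4, rounded up to 277, as stated.
- r = 0.4: 7.84 × 1.2/0.04 + 2 = 237.2, rounded up to 238, as stated.

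All eight tabulated sizes reproduce. Noncentral-t power is 0.805 at n = 280, r = 0.3 and 0.812 at n = 245, r = 0.4. The lost participants are already allowed for in the power calculation, so the issue is bias, not power.

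**2. Routes written for someone who has stopped BHPro.**

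| Measure | Written route | Section |
|---|---|---|
| ADKS (primary), GSE, PRISM-PC | Online within BHPro | 8.1.9, 8.1.8.2, 10.3 |
| Lifestyle questionnaires, with goal setting | Online within BHPro | 8.1.9, 8.1.8.2 |
| GDS, GAD-7, sleep, COVID-19, satisfaction | LORIS link, phone or video help, or paper | 8.1.8.1 |

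The outcome measures and the lifestyle/goal-setting item are separate entries in both 8.1.9 and 8.1.8.2, with separate time estimates (30–45 and 20–30 minutes). Neither section makes one depend on the other.

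**3. Illustrative size.** Let d be the proportion without a final ADKS, m the mean gain among those observed, and D the shortfall in gain among those not observed, in baseline SD. The full-sample mean is (1 − d)m + d(m − D) = m − dD, so a complete-case estimate is too high by d × D. D is an assumption; the documents give no value.

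| D (assumed) | d = 20% | d = 30% |
|---|---|---|
| 0.1 | 0.02 | 0.03 |
| 0.2 | 0.04 | 0.06 |
| 0.3 | 0.06 | 0.09 |
| 0.5 | 0.10 | 0.15 |

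Against the 0.2 SD design effect, that is 0.02/0.2 = 10% up to 0.15/0.2 = 75%.

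**4. What a second route might recover, in one assumed scenario.** Take 88 of 350 without a final ADKS (about 25%), with gains of 0.3 SD in the other 262 and 0.1 SD in the 88.
- Full-sample mean: (262 × 0.3 + 88 × 0.1)/350 = 0.250.
- None observed: 0.300, an excess of 0.05.
- Half recovered: (262 × 0.3 + 44 × 0.1)/306 = 0.271, an excess of about 0.02.

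This supposes that the recovered half is typical of the 88.

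**The case against.** Several counter-arguments have force.

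- **The ADKS is protected by rank.** Section 8.1.9 places it ahead of the GDS and the neuropsychological battery when a stopper will not do everything. This stands, but a ranking does not help someone who refuses the only route offered.
- **No other route is written, but none is forbidden.** Section 8.1.9 refers to the Study Procedures Manual for detail, and that manual is not among the documents. All participants must be able to use e-mail and the internet (7.1), so the added barrier compared with a LORIS link is the BHPro login. Nothing in the documents shows that stoppers refuse it. The point is therefore about what the protocol provides for, not about demonstrated loss.
- **A reader might infer that giving the ADKS obliges stoppers to take part of the treatment again, and so contaminates the primary outcome.** The documents do not support this. Goal setting is a distinct, lower-priority item, and nothing shows that it teaches what the ADKS tests. At an exit visit it is also the last scheduled contact, so it cannot affect a later visit.
- **A reader might take the figures above as the bias in the primary result.** They are not. They are complete-case values on assumed gains, whereas the primary analysis imputes the ITT sample from all time-varying outcomes. Month 6 ADKS can contribute where observed, and chapter completion, a secondary outcome, arguably does too. The planned dropout range also includes people who refuse all contact, whom no extra route would reach. That stoppers gain less is plausible but not documented.
- **One mode for a knowledge scale is a defensible choice.** If mainly stoppers use the second route, mode is largely confounded with stopping. This stands, and favours a self-administered web form, which is closest to the existing mode.
- **Timing.** The SAP is dated November 2024 and already reports missing baseline ADKS data, so an amendment may reach few remaining stoppers.

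**Conclusion.** The point holds as a cheap improvement. As written, capture of the primary outcome in stoppers depends on their re-entering BHPro, while less central questionnaires at Month 12 have three routes. That ties ADKS missingness to disengagement, and no planned sensitivity analysis allows for data missing not at random. The 0.02 to 0.15 SD range rests on two assumptions: that 20–30% lack a final ADKS, and that they gain 0.1 to 0.5 SD less. For those gaps it is an upper bound on what the route could account for, and the residual bias after imputation cannot be derived from the documents. The goal-setting request should be separated from measurement on its own merits, without any claim that it distorts the ADKS.

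**What to change.** In Protocol 8.1.9, 8.1.8.2 and 10.3:
- Keep BHPro as the default. Let stoppers who will not log in complete the ADKS and GSE, then the PRISM-PC and lifestyle items, through a self-administered LORIS survey link, with paper or phone as a last resort.
- Drop goal setting from the assessment of participants who have stopped.
- Record the route used for each assessment.
- Report ADKS capture at each visit by discontinuation status.

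If the Study Procedures Manual already has a fallback, state it in the protocol. If follow-up has closed, the capture report is still possible, and a delta-adjusted sensitivity analysis could be added to SAP 8.1.

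The cost is a short amendment and a small form build: 30 true/false ADKS items and 10 GSE items first, in a survey tool the study already uses. The downside is a possible mode difference. Because route and stopping will largely coincide, the route flag can describe that difference but cannot fully separate it from a true difference in stoppers. An observed score with a known route is still more useful than a missing one.
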